### **6.11.2. Key Secondary Efficacy Analyses**

Secondary comparisons of interest (key secondaries) include:

- TTR: Time to recovery, where recovery is defined as clinical status in states 1, 2, or 3 of the 8-point ordinal scale, censored at Day 28
- Pr.1.D14: proportion of patients with at least 1-point improvement on the NIAID-OS or live discharge from the hospital at Day 4, Day 7, Day 10, and Day 14
- VFD number of ventilator-free days (Day 1 to Day 28)
- NIAID-OS D4/7/10/14: overall improvement on the NIAID-OS evaluated at Day 4, Day 7, Day 10, and Day 14
- DOH: duration of hospitalization (Day 1 to Day 28)
- O2sat D4/7/10/14 proportion of patients with a change in oxygen saturation from <94% to  $\geq 94\%$  from baseline to Day 4, Day 7, Day 10, Day 14; and
- All-cause mortality (Day 1 to Day 28).

**Table KHAA.6.4. Description and Derivation of Primary, Key Secondary, and Associated Supportive Analyses**

Measure	Description	Variable	Derivation / Comment	Definition of Missing
NIAID-OS	Using data from the COVID-19 Clinical Status Assessment, results will be calculated for ordinal scales currently being used in other studies, and in this study, to measure clinical outcomes in patients treated for COVID-19, in particular the NIAID-OS. The NIAID-OS is as follows:	Patients who die or progress to requiring ventilation	Proportion of patients who progress to ventilation or death. In order to be counted as having this event: 
 
• Patients who start at OS 4 or 5 must progress to at least OS 6.
 
• Patients who start at OS 6 must progress to at least OS 7.
 
	Missing if NIAID-OS is missing and the variable status cannot be identified using remaining data.
	1. Not hospitalized, no limitations on activities	Ventilator-free days (days free of invasive mechanical ventilation)	Total number of days patients are alive and have a NIAID-OS less than 7	Missing if patient's NIAID-OS is missing for any day.
	2. Not hospitalized, limitation on activities and/or requiring home oxygen	1-point improvement in OS (at days 4, 7, 10 and 14)	Proportion of patients with baseline NIAID-OS minus NIAID-OS $\geq 1$	Missing if either baseline NIAID-OS is missing or if the observed NIAID-OS is missing on the day of assessment of 1-point improvement
	3. Hospitalized, not requiring supplemental oxygen – no longer requires ongoing medical care: (This would include those kept in hospital for quarantine/infection control, awaiting bed in rehabilitation facility or homecare, etc.)	Time to recovery	Time to reach NIAID-OS 1, 2, or 3 for the first time. The date reached is the first full day that OS 1, 2, or 3 is the patient's maximum OS for the day.	Missing if NIAID-OS is missing and time to event of interest cannot be identified using remaining data
	4. Hospitalized, not requiring supplemental oxygen – requiring ongoing medical care (COVID-19 related or otherwise)	Overall improvement (at days 4, 7, 10, and 14)	NIAID OS	Missing if observed NIAID-OS is missing
	5. Hospitalized, requiring supplemental oxygen	Duration of hospitalization	Total number of days patients have a NIAID-OS of 4, 5, 6, or 7. If the patient died on or prior to Day 28, their duration of hospitalization is considered to be 28 days. On Day 1 the patient's worst ordinal scale between baseline and the rest of Day 1 will be used to define their hospitalization status.	Missing if patient's NIAID-OS is missing for any day
	6. Hospitalized, on noninvasive ventilation or high-flow oxygen devices			
7. Hospitalized, on invasive mechanical ventilation or ECMO				
8. Death				

Measure	Description	Variable	Derivation / Comment	Definition of Missing
		All-cause mortality	Time to death by Day 28. Patients included: ITT population Start date: Baseline date Event date: date of death if death is within 28 days of their baseline date. (That is, if baseline is Day 1, any deaths up to and including Day 28 are included). Censor date: Date of last non-missing OS or visit that is on or prior to Day 28. If there is other information that makes it clear that they were alive at Day 28, they will be censored at Day 28.	Missing if the patient's maximum NIAID-OS is not 8 and patient's NIAID-OS is missing for all days after a particular day
Oxygen Saturation	Measure of the oxygen level of the blood measured by pulse oximetry	Oxygen saturation from <94% at baseline to ≥94% (at days 4, 7, 10 and 14)	Patients included: randomized patients whose oxygen saturation (based on NEWS) is < 94% at baseline. A patient is a responder at Day x if their oxygen saturation is ≥ 94% and their OS is not higher than their baseline OS. Otherwise, they are a non-responder. Patients who are missing data at Day x due to having died are considered to be non-responders.	Missing if either baseline or observed oxygen saturation measurement is missing

Abbreviations: ECMO = extracorporeal membrane oxygenation; NIAID-OS = National Institute of Allergy and Infectious Diseases ordinal scale.

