### Other medical conditions or history

- [13] Require invasive mechanical ventilation, including ECMO at study entry.
- [14] Current diagnosis of active malignancy that, in the opinion of the investigator, could constitute a risk when taking investigational product.
- [15] Have a history of VTE (deep vein thrombosis [DVT] and/or pulmonary embolism [PE]) within 12 weeks prior to randomization or have a history of recurrent (>1) VTE (DVT/PE).
- [16] Anticipated discharge from the hospital, or transfer to another hospital (or another unit), which is not a study site within 72 hours after study entry.

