#### 8.1.3. Other Efficacy Assessments

Several secondary efficacy endpoints of this study are based on clinical assessments and procedures conducted in hospitalized patients with COVID-19 infection. The following table shows these endpoints, their definitions for this study, and measurement method.

Endpoint	Defined as	Measured by
Ventilator-free days	Patient breathing without mechanical	
	ventilation assistance, if the period of	
	unassisted breathing lasts at least 24	
	consecutive hours and the patient does not	
	die	
Recovery	Participant satisfies one of the following	score on NIAID-OS
	three categories from the NIAID-OS:	
	• Hospitalized, not requiring supplemental	
	oxygen – no longer requires ongoing	
	medical care;	
	• Not hospitalized, limitation on activities	
	and/or requiring home oxygen;	
	• Not hospitalized, no limitations on	
	activities (applies to live discharge from	
	hospital to home as well)	
Duration of	Period of time the patient is hospitalized	date of admission to date of
hospitalization		discharge
Oxygen saturation	Measure of the oxygen level of the blood.	pulse oximetry
All-cause mortality	28-day all-cause mortality	score on NIAID-OS
Duration of stay in the	Date of admission to ICU to date of	
intensive care unit (ICU)	discharge from ICU	
Clinical deterioration	One-category increase on the ordinal scale	score on NIAID-OS
	(worsening in patient clinical status)	

Endpoint	Defined as	Measured by
Clinical improvement	One-category decrease on the ordinal scale	score on NIAID-OS
	(improvement of patient clinical status)	
Time to resolution of fever	Time to patients being free of fever for the first time for patients who had fever at baseline. If temperature is assessed multiple times in a day, the maximum temperature will be used.	This includes oral, rectal, tympanic (ear), axilla, forehead, temporal artery temperature measurements.
	Fever resolution is defined by:	
	$\leq$ 36.6°C (axilla)	
	$\leq$ 37.2°C (oral), or	
	≤37.8°C (rectal or tympanic)	
Definitive extubation	When patient is removed from mechanical ventilation	score on NIAID-OS
Non-invasive ventilation/	Administration of ventilatory support	score on NIAID-OS
high-flow oxygen	without using an invasive artificial airway (endotracheal tube or tracheostomy tube). Patients requiring high-flow	
	oxygen breathing support administered	
	through a face mask, nasal mask, or a	
	helmet (includes BiPAP, CPAP)	

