**Table KHAA.6.1. General Methods for Statistical Analysis**

Data Type	Purpose	Analysis
Categorical/discrete data	Summary and descriptive analysis	Number of patients with available data (n), either observed or imputed, at the relevant time point, and will be presented as frequency counts and percentages. Percentages will be calculated using the total number of patients in the analysis population included as the denominator. Percentages will generally be presented to 1 decimal place but will not be presented for zero counts.
	Treatment comparison	Logistic regression analysis
Continuous data	Summary and descriptive analysis	Number of observations, mean, standard deviation (SD), standard error of the mean (SEM), median, 1st quartile, 3rd quartile, minimum, and maximum. The minimum and maximum will be reported to the same number of decimal places as the raw data recorded in the database. The mean, first quartile, median, and third quartile will be reported to 1 more decimal place than the raw data recorded in the database. The SD and SEM may be reported to 2 more decimal places than the raw data recorded in the database. Any exceptions will be noted in the programming specifications. P-values for primary and key secondary analyses will be reported to as many decimal places as needed ( $\geq 5$ ).
	Treatment comparison	Analysis of variance (ANOVA), mixed model repeated measures (MMRM), Wilcoxon rank-sum test
Ordinal data	Treatment comparison	Proportional Odds model, Wilcoxon rank-sum test
Time to event data	Treatment comparison	Log-rank test, Kaplan-Meier curves, Cox proportional hazards. As needed: Fine-Gray model, Max-combo test

Note: the detail of the analysis method defined in Section 6.2.

Change from baseline will be calculated as the visit value of interest minus the baseline value. If the baseline value is missing for a particular variable, then it will not be imputed and the change from baseline and percent change (or percent improvement) from baseline will not be calculated.

For all models, patients will be excluded who do not have the necessary covariates to run the model.

For the primary and key secondary analyses that rely on OS values, the patient's worst ordinal score for the day will be used.

The Per Protocol Set (PPS) will be used if needed for post hoc analyses.

Throughout this document, "Day x" refers to Study Day x.

Additional supportive analyses will be performed as needed.

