### **6.4.1. Infinite Event Time Imputation (IETI)**

For some time-to-event endpoints, if there are competing risks to the event of interest, then the event times censored due to the competing risk will be imputed as infinite.

This imputation method will be applied if the event of interest is in the opposite direction of death (e.g., recovery or improvement). For time to recovery or time to improvement, all deaths

within 28 days will be considered censored at Day 28 with respect to time to event of interest. Conceptually, a death corresponds to an infinite time to event of interest, but censoring at any time greater than or equal to Day 28 gives the same answer as censoring at Day 28; both correspond to giving death the worst rank.

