## 6.6. Multiple Comparisons/Multiplicity

Multiplicity controlled analyses will be performed on the primary and key secondary endpoints to control the overall family-wise Type I error rate at a 1-sided  $\alpha$  level of 0.025. The graphical multiple testing procedure described in Bretz et al. (2011) will be used. The graphical approach is a closed testing procedure; hence it strongly controls the family-wise error rate (FWER) across all endpoints (Alosh et al. 2014).

[figure not shown]
See [Figure KHAA.6.1](#) for the graphical testing scheme for this study. This scheme allows for some  $\alpha$  to be sent to the key secondary analyses if Population 1 achieves statistical significance (see next paragraph). Note that for the 2 primary populations the scheme is slightly different from what is in the protocol. As the testing scheme only impacts interpretation of the results and not the actual analysis, there is no plan to update the protocol.

If Population 2 is rejected at  $\alpha_2$ , Population 1 will be tested at level  $\alpha$ , otherwise Population 1 will be tested at level  $\alpha_1$ . If Population 1 is rejected, each of the gated secondaries will be tested in order until one is not rejected as depicted in [Figure KHAA.6.1](#). The key secondaries will be tested at level  $\alpha_1$  if Population 1 was rejected or at level  $\alpha$  if both Population 1 and Population 2 were rejected. Finally, if Population 1 and all secondaries are rejected at level  $\alpha_1$ , but Population 2 was not rejected at level  $\alpha_2$ , Population 2 will be tested again at level  $\alpha$ .

The testing scheme will provide a strong control of Type-I error for the study at a 1-sided 0.025 level and is based on the closed testing principle (Marcus et al. 1976). The testing scheme is parametric, where the known correlation is accounted for between the 2 test statistics  $z_1$  and  $z_2$ . The initial significance levels for the Primary endpoints Population 1 ( $\alpha_1$ ) and Population 2 ( $\alpha_2$ ) will be computed using the fact that their test statistics have a correlation of  $\sqrt{p}$  where  $p$  is the percentage of Population 2 within Population 1 observed in the final analysis data set and a 0.99 weight on Population 1 and 0.01 weight on Population 2. The two significance levels will be computed using the R package gMCP.

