**Table KHAA.6.5. Description of Primary, Key Secondary, and Associated Supportive Analyses**

Measure	Variable	Population	Analysis Method	Time Point	Analysis Type
NIAID-OS	Proportion of patients who died or progressed to non-invasive ventilation or high-flow oxygen (OS $\geq$ 6)	ITT: Population 1 - all randomized patients	Logistic regression using MI	By Day 28	Primary analysis
		ITT: Population 2 – patients who, at baseline, require oxygen supplementation and are not receiving dexamethasone or other systemic corticosteroids for the primary study condition.	Logistic regression using MI	By Day 28	Primary analysis
		ITT	Logistic regression using LOCF	By Day 28	Supportive analysis
		ITT: Population 2	Logistic regression using LOCF	By Day 28	Supportive analysis
		Safety Population	Logistic regression using MI	By Day 28	Supportive Analysis
		ITT Population, excluding patients who die within 24 hours of baseline and have Do Not Resuscitate (DNR) or Do Not Intubate (DNI) orders	Logistic regression using MI	By Day 28	Sensitivity Analysis
		Ventilator free days (VFD)	ITT	ANOVA using MI	By Day 28
	Wilcoxon rank-sum test using LOCF			By Day 28	Supportive analysis
	Proportion of patients with 1-point improvement	ITT	Logistic regression using MI	Day 4, 7, 10, 14	Key secondary analysis
			Logistic regression using LOCF	Day 4, 7, 10, 14	Supportive analysis

Measure	Variable	Population	Analysis Method	Time Point	Analysis Type
	Time to recovery	ITT	Log-rank test using IETI	By Day 28	Key secondary analysis
			Cox proportional hazards model using IETI	By Day 28	Supportive analysis
			Max-combo test using IETI (if needed)	By Day 28	Supportive analysis
NIAID-OS	Overall improvement	ITT	Proportional odds model using MI	Day 4, 7, 10, 14	Key secondary analysis
			Proportional odds model using LOCF	Day 4, 7, 10, 14	Supportive analysis
	Duration of hospitalization	ITT	ANOVA using MI	By Day 28	Key secondary analysis
			Wilcoxon rank-sum test LOCF	By Day 28	Supportive analysis
	All-cause mortality	ITT	Log-rank test	By Day 28	Key secondary analysis
			Cox proportional hazards model	By Day 28	Supportive analysis
Safety					
			Log-rank test	By Day 28	Supportive analysis
			Cox proportional hazards model	By Day 28	Supportive analysis
Oxygen Saturation	Proportion of patients with change in oxygen saturation from <94% at baseline to $\geq$ 94% at the observed time point	ITT	Logistic regression using LOCF	Day 4, 7, 10, 14	Key secondary analysis

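### The SAP credits ventilator-free days accrued before death, protocol 8.1.3 makes them conditional on the patient not dying, and the SAP neither flags nor explains the difference

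*SAP*

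**What the plan says.** **Protocol.** The table in section 8.1.3 defines VFD as breathing without ventilator assistance, with two conditions: the spell lasts at least 24 hours, and the patient survives. The cell runs "consecutive hours and the patient does not", and the next word is die. No time frame and no score for deaths are given, and the measurement column is blank for this row.

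**SAP derivation.** Table KHAA.6.4 gives "Total number of days patients are alive and have a NIAID-OS less than 7". Appendix 3 confirms the reading: it describes VFD per the main SAP as days both alive and off mechanical ventilation. SAP 6.1 adds that "the patient's worst ordinal score for the day will be used". In effect this keeps the protocol's 24-hour condition, since any ventilation during a day removes that day. Nothing corresponds to the survival condition. In the same table, duration of hospitalization does have a death rule: "If the patient died on or prior to Day 28, their duration of hospitalization is considered to be 28 days".

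**Role.** VFD is a key secondary endpoint (SAP 6.11.2). Under SAP 6.6, once Population 1 is rejected, "each of the gated secondaries will be tested in order until one is not rejected". Table KHAA.6.5 lists ANOVA using multiple imputation (MI) for VFD and marks a Wilcoxon test using last observation carried forward (LOCF) as supportive, so I take the ANOVA as the key test.

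**Change record.** For Table KHAA.6.4 the SAP revision history says only that derivation details were added. The one departure from the protocol that the SAP's analysis text acknowledges is the testing scheme for the two primary populations (6.6).

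**Appendix 3.** For the Addendum 5 patients, analyses 1 to 4 are assigned logistic regression with LOCF. Analyses 3 and 4 are VFD and duration of hospitalization.

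**The concern.** The two documents define different quantities under one name, and a programmer working from each would derive different values for almost every patient who dies. This is not a corner case. Protocol exclusion criterion 13 reads "Require invasive mechanical ventilation, including ECMO at study entry", so main-study patients enter below score 7. Anyone who dies therefore has credited days, unless intubation or death comes on Day 1.

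At stake is the meaning, and possibly the result, of an alpha-controlled secondary endpoint. In the ANOVA, a death costs 28 minus its credited days instead of 28. In the supportive Wilcoxon test, some deaths rank above surviving patients who were ventilated. Depending on the order in Figure KHAA.6.1, the VFD result also decides whether later key secondaries are reached.

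The Appendix 3 item is separate and exploratory: logistic regression does not fit a count of days.

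**Working it through.** Neither document gives a mean, SD or power for VFD, so there is no stated figure to reproduce.

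**1. Individual scores (exact).** Under the worst-score rule the day of death is score 8 and earns nothing. A never-ventilated patient dying on Day d has d − 1 credited days and loses 28 − (d − 1) = 29 − d. This is the largest credit possible for that day of death. A survivor ventilated v days scores 28 − v. The death scores higher when d − 1 > 28 − v, that is, v ≥ 30 − d.

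| Death on | SAP score | Days lost (deaths = 0: 28) | Scores above survivors ventilated |
|---|---|---|---|
| Day 14 | 13 | 15 | 16 or more days |
| Day 21 | 20 | 8 | 9 or more days |
| Day 28 | 27 | 1 | 2 or more days |

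Example: a Day 21 death scores 20; a survivor ventilated 12 days scores 28 − 12 = 16. With deaths = 0 the scores are 0 and 16. An intubated death gets less: dying on Day 20 after ventilation on Days 8 to 19 scores 7.

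**2. Arm means (exact, unadjusted).** Let m be the death proportion, c the mean credited days per death, and w the survivors' ventilated days per randomized patient.
- Deaths = 0: mean = 28(1 − m) − w
- SAP rule: mean = 28(1 − m) − w + m·c
- So difference (SAP rule) = difference (deaths = 0) + (mB·cB − mP·cP), with B baricitinib and P placebo.

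**3. Size on assumed inputs.** The documents do not give c. I take 5, 10 and 15, the same in both arms.
- Weight of a death relative to deaths = 0: (28 − c)/28 = 23/28, 18/28, 13/28, or 82%, 64%, 46%.
- Shift per 1-point mortality difference: 0.01 × c = 0.05, 0.10, 0.15 days.
- Contribution of an assumed 4-point mortality difference, w held equal: 0.04 × (28 − c) = 0.92, 0.72, 0.52 days, against 0.04 × 28 = 1.12.
- Timing alone: equal 10% mortality, identical survivors, cB = 13 and cP = 10 give 0.10 × (13 − 10) = 0.30 days under the SAP rule and 0 with deaths = 0.

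**4. Power under each rule (all inputs assumed).** 700 per arm, one-sided 0.025, normal approximation: power = 1 − Φ(1.96 − Δ/SE), SE = SD·√(2/700). Ventilated survivors have 4 to 24 ventilated days, uniform (mean 14). Credited days are uniform within 4 of c. There are no missing data and no covariates.
- *Ventilation benefit only:* mortality 10% in both arms, survivors ventilated 12% versus 7%. Δ = 0.90 × 0.05 × 14 = 0.63 under both rules.
- *Mortality benefit only:* mortality 13% versus 9%, 8% of survivors ventilated in both arms. Mean survivor score is 28 − 0.08 × 14 = 26.88. Δ = 0.04 × (26.88 − c) = 0.875, 0.675, 0.475 under the SAP rule, and 0.04 × 26.88 = 1.075 with deaths = 0.

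| | SAP, c = 5 | SAP, c = 10 | SAP, c = 15 | Deaths = 0 |
|---|---|---|---|---|
| Ventilation only: SD | 7.8 | 6.6 | 5.6 | 9.1 |
| Ventilation only: power | 33% | 43% | 56% | 25.5% |
| Mortality only: SD | 7.9 | 6.6 | 5.5 | 9.3 |
| Mortality only: power | 54% | 48% | 37% | 58% |

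The mortality row depends on the 8%: over 7% to 12%, the c = 15 figure runs from about 39% to 30%. Neither rule is uniformly better.

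**The case against.** The best defence is that the protocol's line is terse and leaves detail to the SAP. Protocol 9.4.1 says the VFD comparison will be described further there, and 9.4 calls the SAP the more technical document. The duty in 9.4 to justify changes concerns analysis methods, and an endpoint derivation is arguably something else. The survival clause could also mean only survival through the 24-hour spell. The SAP count is fully specified and openly says alive, and mortality is tested separately as a key secondary.

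Much of this stands. Choosing between the two quantities is a legitimate estimand decision. But leaving detail to the SAP does not cover dropping a stated condition in silence. The narrow reading makes the clause redundant, because a patient breathing unassisted for 24 hours is alive.

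A reader might infer more, without support:
- *That the protocol prescribes zero for deaths.* It does not; no score is written.
- *That VFD is the SAP's lone exception.* Practice is mixed. ICU stay and days on supplemental oxygen (Table KHAA.6.6) also keep pre-death days as observed. Duration of hospitalization needs its rule, since an early death would otherwise look like a short stay.
- *That the do-not-resuscitate or do-not-intubate sensitivity analyses show the credit to be large.* The Table KHAA.6.5 analysis concerns patients who "die within 24 hours of baseline and have Do Not Resuscitate (DNR) or Do Not Intubate (DNI) orders", and 6.11.4 uses 48 hours from screening. Such early deaths carry almost no credited days.

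**Conclusion.** The mismatch is real and should be fixed, but it is moderate. The difference in definition and the reversal of individual scores follow from the documents. The effect on the arm difference is known only as a formula; every arm-level number above rests on assumed mortality and credited days.

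The direction is not fixed. With lower mortality on baricitinib and similar credited days per death, the SAP rule understates the VFD benefit. With equal mortality and later deaths on baricitinib, it shows a difference that deaths = 0 would not. A reader might infer type I error inflation or a threat to study success. Neither follows: both arms are scored by the same rule, and success rests on the primary endpoint in the two populations.

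The Appendix 3 error is plain, but confined to exploratory analyses.

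**What to change.** Before unblinding, reconcile SAP Table KHAA.6.4 with protocol 8.1.3 in one of two ways.

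1. **Adopt deaths = 0.** VFD is 0 for any patient who dies on or before Day 28, including a death imputed under Appendix 2; otherwise it is the number of days with NIAID-OS below 7. Keep the current count as supportive.
2. **Keep the current count as key.** Rename it *days alive and free of invasive ventilation*, record the departure from protocol 8.1.3 with its reason, and prespecify the deaths = 0 version as a sensitivity analysis with the same ANOVA using MI.

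In Appendix 3, replace logistic regression for VFD and duration of hospitalization with ANOVA using LOCF, adjusted for age group and region. Table KHAA.6.12 already uses ANOVA with LOCF for both endpoints.

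No new data are needed. The second option costs one extra analysis. The first costs power if the benefit is on ventilation only (25.5% against 33% to 56% in the illustration).

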## 8.1. Efficacy Assessments

## 8.1.1. COVID-19 Clinical Status Assessment

The COVID-19 Clinical Status Assessment will be used to collect components needed to derive scores for the ordinal scales used in this study. This assessment will also collect the use of proning and reason for discontinuation of invasive mechanical ventilation.

The assessment will be completed on each day of the study by entering the assessment for the previous day (that is, midnight to midnight; 00:00 - 23:59 [24 hour clock]).

On Day 1, the patient's status at randomization will be reported.

On Day 2 the status will be reported for the period from randomization to midnight on Day 1.

The patient's clinical status will be captured daily through Day 29.

The hospitalization portion of the patient's clinical status will be completed daily, regardless of patient's discharge status or patient contact.

The patient's clinical status reflecting data for Day 28 (midnight to midnight) will be recorded in the Day 29 eCRF.

A clinical status assessment will be conducted via telephone visit for Day 60.

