**Description and Derivation of Other Secondary Outcomes**

Measure	Variable	Derivation / Comment	Definition of Missing
	Number of days with supplemental oxygen use	Total number of days patients' NIAID-OS is $\geq 5$	Missing if any observed NIAID-OS is missing.
	Proportion of patients in each severity category	Total proportion of patients in each NIAID-OS category at particular time points	Missing if observed NIAID-OS is missing at particular time point.
	Patients with at least 2-point improvement on the NIAID-OS or live discharge from the hospital	Proportion of patients whose baseline NIAID-OS - observed NIAID-OS $\geq 2$	Missing if observed NIAID-OS is missing or if observed NIAID-OS is $\geq 3$ and baseline NIAID-OS is missing
	Patients with at least 1-point improvement on the NIAID-OS or live discharge from the hospital	Proportion of patients whose observed NIAID-OS is $\leq 2$ or whose baseline NIAID-OS - observed NIAID-OS $\geq 1$	Missing if observed NIAID-OS is missing or if observed NIAID-OS is $\geq 3$ and baseline NIAID-OS is missing
Intensive Care Unit (ICU) stay	Duration of stay in the intensive care unit (ICU)	Total number of days spent in the ICU plus days from death up to and including Day 28.	Missing if status of ICU stay is missing for any day for the patients and the patient is alive.
Fever	Time to resolution of fever	
Time to patients being free of fever for the first time for patients who had fever at baseline.
 
Fever resolution is defined by:
 
 
• <math>\leq 36.6^{\circ}\text{C}</math> (axilla, forehead)
 
• <math>\leq 37.2^{\circ}\text{C}</math> (oral cavity), or
 
• <math>\leq 37.8^{\circ}\text{C}</math> (rectum, ear, temporal artery)
 
 
If temperature is assessed multiple times in a day, fever will be considered to be resolved if all of the measurements fall in the “fever resolution” ranges defined above
	Missing if fever status is missing or baseline fever status is missing and time to event of interest cannot be identified using remaining data.
National Early Warning Score (NEWS)	Mean change	
Mean of observed NEWS – NEWS at baseline
 
NEWS will be calculated using aggregate score approach in Royal College of Physicians [WWW].
	Missing if either baseline or observed NEWS component is missing.

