## 2) Addendum 5 Analyses (for Patients who are OS 7 at Baseline)

The following analyses are planned for randomized patients in Addendum 5 with baseline OS = 7. Patients who discontinue on the day of randomization with no baseline or postbaseline OS data will not be included.

1. NIAID-OS D4/7/10/14/28: overall improvement on the NIAID-OS evaluated at Day 4, Day 7, Day 10, 14 and Day 28
2. Proportion of patients with at least 1-point improvement on the NIAID-OS or live discharge from the hospital at Day 4, Day 7, Day 10, 14 and Day 28
3. Number of days alive and free of mechanical ventilation (VFD per main SAP), Day 1 to Day 28
4. Duration of hospitalization (Day 1 to Day 28)
5. Time to recovery (by Day 28)
6. All-cause mortality (Day 1 to Day 28).

Analyses 1-4 will use logistic regression with LOCF methodology. Analyses 5-6 will use time-to event methodology. All will follow the same methodology as the main SAP, except that treatment comparisons will be adjusted for baseline age group (<65, ≥65 years) and region rather than all the baseline stratification variables given in Section 6.1.4.

Patient disposition, patient characteristics and safety analyses will follow the main SAP to the extent possible (see Sections 6.7, 6.8, and 6.13).

The following table gives additional analyses for the Addendum 5 patients, utilizing their Day 60 data.

Variable	Population	Analysis Method	Time Point	Groups/Subgroups
Observed OS values at Day 60.	ITT population with a baseline NIAID OS and a value at the Day 60 Visit	Descriptive statistics.	At the Day 60 visit.	Overall (OS 7) 
 
• Baseline corticosteroid status (see Section 6.1.4)
 
• Age group (<65, ≥65)
 

All-cause mortality	ITT population with a baseline NIAID OS	Time to death from all causes, all time on study. Event dates are date of death for patients who died. Censor dates are last known information that indicates patient was alive. Patients who die after the visit window for Day 60, will be censored at the last date of their Day 60 visit window. KM curves and standard summary statistics (see Section 6.2.3) will be generated.	From baseline to end of study participation.	

Demographics, disposition, and safety analyses for Addendum 5 patients will mirror the main study to the extent possible. The main comparative safety analyses will be based on data from baseline to Day 28. There will be separate analyses of FEAEs, as described in Section 6.13.

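### Duration of hospitalization, a gated key secondary, leaves out days at NIAID-OS 3 although the SAP itself classes OS 3 as hospitalized

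*SAP*

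**What the plan says.** SAP 6.11.2 lists duration of hospitalization (Day 1 to Day 28) among the key secondaries. SAP 6.6 tests these in sequence once Population 1 is rejected.

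The derivation is in Table KHAA.6.4: "Total number of days patients have a NIAID-OS of 4, 5, 6, or 7". For deaths it adds: "If the patient died on or prior to Day 28, their duration of hospitalization is considered to be 28 days". For Day 1 it says that the patient's "worst ordinal scale between baseline and the rest of Day 1 will be used to define their hospitalization status".

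The scale printed in the same table has only two non-hospitalized living states, OS 1 and OS 2. OS 3 is a hospitalized state for patients who need neither oxygen nor further medical care, and the table explains: "This would include those kept in hospital for quarantine/infection control, awaiting bed in rehabilitation facility or homecare".

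Protocol 8.1.3 defines the endpoint as "Period of time the patient is hospitalized", measured between the admission and discharge dates.

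**The concern.** A day that the SAP classes as hospitalized adds nothing to the hospitalization count. Two survivors with different discharge dates can receive the same score, and a patient who never leaves hospital by Day 28 can score well below 28.

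Among living patients, OS 4-7 is the exact complement of the recovery states OS 1-3. The variable therefore counts days spent outside a recovery state, with death set to 28, and it overlaps heavily with time to recovery, which is already a key secondary. A rejection would be reported as a shorter hospital stay when the variable tested does not measure stay.

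The same derivation feeds the subgroup analyses in Table KHAA.6.12 and the Addendum 5 item "Duration of hospitalization (Day 1 to Day 28") in Appendix 3.

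**Working it through.** The SAP gives no figure for this endpoint, so there is nothing to reproduce. The check compares the definitions and then works through the rule.

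**Is OS 3 in hospital?**

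- The scale wording in Table KHAA.6.4 says yes.
- Table KHAA.6.6 agrees. Its 1-point improvement or live discharge variable begins "Proportion of patients whose observed NIAID-OS is $\leq 2$ or whose baseline NIAID-OS", so discharge corresponds to OS 2 or lower.
- No reason for leaving out OS 3 was found in 6.11.2, Appendix 3 or the revision history. The revision history says only that derivation details were added for several variables.

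**Effect on one patient.** For a survivor:

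- hospital days within Day 1-28 = days at OS 3-7
- SAP score = days at OS 4-7
- shortfall = days at OS 3

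A death by Day 28 scores 28 under either count.

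| Path over Days 1-28 | SAP score (OS 4-7) | OS 3-7 count |
|---|---|---|
| OS 5 Days 1-10, then discharged | 10 | 10 |
| OS 5 Days 1-10, OS 3 Days 11-17, then discharged | 10 | 17 |
| OS 5 Days 1-10, OS 3 Days 11-28 | 10 | 28 |
| OS 5 Days 1-10, then dies | 28 | 28 |

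The shortfall for a survivor runs from 0 to at most 27 days (OS 3 from Day 2 through Day 28).

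**Effect on an arm mean.** Shortfall = (share of patients with OS 3 days) x (mean OS 3 days among them). The documents give neither input. Assumed ranges of 5-40% and 1-7 days give 0.05 x 1 = 0.05 days to 0.40 x 7 = 2.8 days.

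**Effect on the treatment difference.** Let M3 be an arm's mean number of OS 3 days, taken as 0 for deaths by Day 28. Because the SAP mean equals the OS 3-7 mean minus M3, the error in baricitinib minus placebo is:

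M3(placebo) - M3(baricitinib)

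Two hypothetical cases, each a one-day shift in 25% of the baricitinib arm (0.25 x 1 = 0.25 days):

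- OS 3 is reached one day earlier and the discharge date does not change: SAP difference -0.25, true difference 0.
- The OS 3 stay is one day shorter and the recovery day does not change: SAP difference 0, true difference -0.25.

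**Scale.** The planned 1400 patients at 1:1 give 700 per arm. With an assumed SD of 6 to 10 days, SE = SD x sqrt(2/700), which is 0.32 to 0.53 days. An error of 0.25 days is then 0.25/0.32 = 0.8 SE down to 0.25/0.53 = 0.5 SE.

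**The case against.** The strongest defence is that OS 3 was left out on purpose. Recovery is defined as OS 1-3 throughout both documents, and a stay for quarantine or while waiting for a rehabilitation place reflects local practice more than illness. Not counting it could be a sensible choice. But the SAP does not say that this was the intent, and neither the endpoint's name nor the protocol definition describes such a variable. If it was intended, it needs its own name and a stated reason.

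A second objection is that counting OS 3-7 still does not give admission-to-discharge time. Days before Day 1 and after Day 28 remain uncounted, and a patient who dies on Day 3 still scores 28. This is true, but the window and the death score are stated conventions. They do not justify dropping in-hospital days of survivors inside the window.

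Three narrower points stand:

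- Calling the SAP variable days alive and not recovered is inexact for relapses. A patient who reaches OS 3 and returns to OS 5 has recovered under the time-to-recovery rule, yet the later OS 5 days count.
- The OS 2 or lower coding of discharge appears in one other-secondary row, and the Day 1 sentence governs Day 1 only. Both corroborate; the scale wording carries the argument.
- No material effect on the treatment comparison has been shown. If mean OS 3 days are equal in the two arms, the difference is unbiased. The endpoint's place in the testing sequence could not be checked either, because the testing figure is missing from the text reviewed.

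**Conclusion.** The concern holds. Applied exactly as written, the rule gives a wrong number of hospital days for every survivor with at least one day at OS 3, in a gated key secondary. That conclusion rests on the documents' own definitions and needs no assumption.

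The consequence for the trial result is not known. The treatment difference would be overstated if baricitinib lengthens time at OS 3 (earlier recovery, same discharge date) and understated if it shortens time at OS 3. The per-arm range of 0.05 to 2.8 days and the 0.5 to 0.8 SE illustration depend on assumed OS 3 frequency, duration and SD. The primary endpoint is untouched and Type I error is not inflated; what is at stake is the meaning of a rejection. It should be fixed.

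**What to change.** In Table KHAA.6.4, define duration of hospitalization as the number of days from Day 1 to Day 28 at NIAID-OS 3, 4, 5, 6 or 7, and keep 28 days for death on or before Day 28. Use the same derivation for the subgroup analyses (Table KHAA.6.12) and the Addendum 5 analysis.

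If the OS 4-7 count is still of interest, report it as supportive under an exact name, such as days at OS 4-7 with death = 28, and state why OS 3 is left out.

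The cost is one added category in the derivation table and the matching program change. Protocol 8.1.1 already records status daily through Day 29 and states: "The hospitalization portion of the patient's clinical status will be completed daily, regardless of patient's discharge status or patient contact". The imputation model in SAP Appendix 2 already covers all eight states, so no new data or imputation work is needed.
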